8.7.3 Dose Re-escalations for Crenolanib during induction and maintenance

In patients for whom the dose has been reduced due to toxicity, the dose may be re-escalated provided the patient has shown no clinical benefit and has remained free of toxicity requiring dose adjustments for at least 1 month. Escalation will be made by 1 dose-level increments only, and not more frequent than every cycle to a max of 220 mg/m²..

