7.2 Study Design

Fourteen relapsed/ refractory AML patients with FLT3 activating mutations will be treated with crenolanib daily as reinduction until they meet one of the criteria for discontinuation. After HSCT, patients who received crenolanib prior to transplant and achieved response may continue on study post-transplant with maintenance crenolanib. Until they meet one of the criteria for discontinuation. Subject efficacy evaluations will be performed at scheduled time points. These include: monthly bone marrow biopsy in the first two months, and then every three months for as long as criteria for CR/CRi is maintained. At loss of CR/CRi, bone-marrow biopsy will be performed only as clinically indicated to exclude toxicity issues such as pancytopenia due to study drug versus myelosuppression from progressive AML. Subjects' best clinical response will be recorded, as well as the response at 2 months. Subjects not in CR/Cri by the end of month 2 but showing clinical benefit will be allowed to continue therapy at the discretion of the physician.

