8.7 Dosing and Dose Modification of Crenolanib

Protocol: ARO-004

Toxicities will be graded using the NCI CTCAE, Version 4.03 (see partial representation in Appendix VI).

All patients with relapsed/refractory AML will receive crenolanib induction therapy at a starting oral dose of 200mg/m²/day divided three times a day (preferably every eight hours) continuously for 28 days for each cycle of treatment. Study drug should be taken at least 30 minutes prior to or following a meal..

Crenolanib will be held starting 72 hours prior to start of planned conditioning for HSCT. Study drug will be held for a minimum of 30 days post infusion of stem cells (day of HSCT).

Post HSCT crenolanib will resume at the dose level last tolerated prior to HSCT.

BSA will be capped at $2m^2$ for large patients and $1.5m^2$ for small patients. Therefore the highest starting study drug dose will be 400 mg/day ($2m^2 \times 200 \text{mg/m}^2/\text{day}$) and lowest drug dose will be 240 mg/day ($1.5m^2 \times 160 \text{mg/m}^2/\text{day}$ -see dose reduction scheme table 8.4).

Because dosing increments based on BSA may not result in uniform doses given TID, the sponsor will provide detailed dosing instructions to the site. Upon enrollment, the site will provide the sponsor the patient's height, weight and BSA. Along with the acknowledgement of enrollment, the sponsor will provide the site with a dosing information sheet (Appendix XV) on which will be the calculated starting dose (dose level 0) with instructions for how much drug should be taken at each TID ingestion. Similar instructions will be provided on the dosing instruction sheet for dose level (+1), (-1) and (-2) should the patient require dose modification while participating on the study.

Patients currently enrolled under protocol version 3 can be continued at their current dose and dose escalated as defined in this protocol version 4 if without grade 3 or 4 toxicity and lack of response to study drug at the current dose.

Patients are strongly encouraged to be premedicated as for moderate to highly emetogenic therapy per ASCO 2011 guidelines. Patients will complete a daily diary to record the date, time and amount (number of tablets) of crenolanib taken, and if it was taken with or without food. (Appendix III)

Dose Escalation during induction and maintenance

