There will be one level dose escalation allowed for patients who do not experience grade 3 or 4 toxicity and who have no response based on investigator evaluation.

Table 8.2: Dose escalation guidance

Dose level	Crenolanib dosing
0	$200 \text{ mg/m}^2/\text{day}$
+1	$220 \text{ mg/m}^2/\text{day}$

Dose escalation can occur as early as cycle 1 day 15.

Protocol: ARO-004

Counting Cycle Days: If drug is held or a dose is missed, the missed/held dose should not be made up. Dosing will resume with the next scheduled dose. The patient should enter in the diary the doses as missed. If drug is held or missed for a day or more, the cycle should continue as if uninterrupted. Counting days of a cycle should be ongoing without disruption. The start of cycle 1 is denoted by the ingestion of study drug. The scheduled procedures/visits should comply with the study calendar regardless of amount of study drug administered in a 28 day cycle.

8.7.1 Dose Reductions for Crenolanib for Non-hematologic Toxicities During Reinduction and Post Allogeneic Transplant

Toxicities will be graded using the NCI CTCAE, Version 4.03 (Appendix VI).

For patients receiving crenolanib for reinduction therapy: Dose reductions for non-hematologic toxicities except nausea, vomiting, and diarrhea due to crenolanib will be done according to the schema in Table 8.3. Dose reductions are summarized in Table 8.4 and reductions below 160mg/m²/day will lead to withdrawal from the study drug, in which case the patient will stop taking crenolanib, but will still be followed for outcomes as outlined in 8.12.

Table 8.3. Based on NCI CTCAE v4.03, Crenolanib Dose Reduction for Non Hematologic Toxicities Except Nausea, Vomiting, and Diarrhea related to study drug. Use toxicity grade at time of start of next planned cycle. Reassessment may be performed weekly to determine when to restart drug or dose modify. A 28-day deferment window is allowed to assess toxicities.

Toxicity (NCI Criteria)	Dose modification for patients taking crenolanib as reinduction
Grade 1 or 2	No dose modification
Clinically significant or persistent grade 2 despite optimal therapy	Hold drug until toxicity resolves to grade 1 or less. Restart drug at same dose level (Table 8.4).
Grade 3 or 4	Hold drug until toxicity resolves to grade 1 or less. Restart drug at next-lower_dose level (Table 8.4).

Table 8.4. Dose levels of Crenolanib During Reinduction

Dose Level	Crenolanib Daily Dose
Baseline	200mg/m ² /day

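### As worded, section 8.7.3 lets a patient reduced from 200 mg/m²/day for grade 3–4 non-hematologic toxicity climb to 220, a level section 8.7 allows only without such toxicity

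*Combined protocol and SAP*

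**What the plan says.** **First escalation (section 8.7, Table 8.2).** Level 0 is 200 mg/m²/day and level +1 is 220. The rule is: "There will be one level dose escalation allowed for patients who do not experience grade 3 or 4 toxicity and who have no response", the response being judged by the investigator. For patients carried over from protocol version 3, the same section permits escalation "if without grade 3 or 4 toxicity and lack of response to study drug at the current dose".

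**Reduction (section 8.7.1, Tables 8.3 and 8.4).** The scope is: "Dose reductions for non-hematologic toxicities except nausea, vomiting, and diarrhea due to crenolanib will be done according to the schema in Table 8.3". In that table, persistent or clinically significant grade 2 toxicity leads to a hold and a restart at the same level. Only grade 3 or 4 leads to a restart one level down, which from 200 is 180. The table is headed with an instruction to use the grade present when the next cycle is due to begin, with weekly reassessment possible.

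**Re-escalation (section 8.7.3).** A patient reduced for toxicity may go back up "provided the patient has shown no clinical benefit and has remained free of toxicity requiring dose adjustments for at least 1 month". The pace and ceiling are: "Escalation will be made by 1 dose-level increments only, and not more frequent than every cycle to a max of 220" mg/m².

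**Continuation (section 7.2).** "Subjects not in CR/Cri by the end of month 2 but showing clinical benefit will be allowed to continue therapy", at the physician's discretion. The section is silent on patients without clinical benefit.

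**The concern.** The two rules on reaching 220 differ. Section 8.7 screens out patients with grade 3 or 4 toxicity. Section 8.7.3 governs patients who have already had toxicity, yet it sets its ceiling at 220 rather than at the dose where the toxicity occurred, and it does not refer back to the 8.7 condition. For the toxicities covered by Table 8.3, the patients reduced are exactly those with grade 3 or 4 events, so 8.7.3 appears to readmit the group that 8.7 excludes.

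What is at stake is patient safety and consistency between sites. A patient could be taken above the dose that caused a severe event, and two sites could treat the same patient differently while each cited the protocol. The dosing sheet in Appendix XV lists the 220 dose for each patient with no condition beside it. Dose-reducing toxicity has already been seen: section 8.6 reports two patients reduced for grade 3 and 4 transaminitis at 100 mg TID. No sample-size, power or endpoint figure depends on this point.

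**Working it through.** **1. The dose path.** The inputs are Tables 8.2, 8.3 and 8.4 and section 8.7.3.

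| Step | Rule | Dose (mg/m²/day) |
|---|---|---|
| Start | 8.7 | 200 |
| Grade 3–4 non-hematologic event (not nausea, vomiting or diarrhea), hold, restart | Tables 8.3 and 8.4 | 180 |
| At least 1 month without dose-adjusting toxicity, no clinical benefit | 8.7.3 | 200 |
| Next cycle at the earliest, same conditions | 8.7.3 | 220 |

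Under the 8.7 rule read without qualification, the last step is not available to this patient. Reductions for blood counts, nausea, vomiting or diarrhea follow other rules and are outside this point. If the toxicity occurred at 220, the 8.7.3 ceiling returns the patient to the same dose, not above it.

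**2. Size of the step.** Daily dose = BSA × level. Section 8.7 caps BSA at 2 m² and 1.5 m².

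- Plan's own figure: 2 × 200 = 400 mg/day, which reproduces "Therefore the highest starting study drug dose will be 400 mg/day". That sentence limits the starting dose only.
- At 2 m²: 2 × 220 = 440, against 400 mg/day.
- At 1.5 m²: 1.5 × 220 = 330, against 1.5 × 200 = 300 mg/day.
- Relative step: 220/200 − 1 = 10%.

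**3. Timing.** Let *t* be the study day of the reduction decision and *h* the days on hold. Take 1 month as 28 days at 180, then one 28-day cycle at 200. The patient returns to 200 on day *t* + *h* + 28 and reaches 220 on day *t* + *h* + 56.

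| *t* | *h* | To 200 | To 220 |
|---|---|---|---|
| 1 | 0 | day 29 | day 57 |
| 15 | 7 | day 50 | day 78 |
| 29 | 0 | day 57 | day 85 |
| 29 | 28 | day 85 | day 113 |

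The first row is a limiting case: toxicity on day 1 and no hold at all, although Table 8.3 requires a hold until grade 1 or less. If the table's next-cycle grading is applied, the decision falls at about day 29, so 220 comes at about day 85 plus any hold. In every row the step to 220 falls after two 28-day cycles (day 56).

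**4. Who is still on drug by then.** Section 8.7.3 requires no clinical benefit. After month 2, section 7.2 expressly continues patients not in CR/CRi only if they do have clinical benefit. The two conditions nearly exclude each other. They do not fully close the path, because 7.2 works by implication and section 6.3.1 does not list non-response among the reasons to stop study drug. Patients on post-transplant maintenance are in remission (section 8.3), so they would rarely count as having no clinical benefit.

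**The case against.** The best reply is that re-escalation means going back to a level already held. The 220 ceiling would then serve patients who had been raised to 220 and later reduced. For anyone who had never taken 220, the move from 200 would be a first escalation under 8.7, which bars it after grade 3–4 toxicity. This reading is natural and would reconcile the two sections. But 8.7.3 does not state it, and under it a patient with grade 3–4 toxicity at 220 could still return to 220.

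A second reply is that 8.7 tests current tolerance only. The sentence on version 3 patients ends with a reference to the current dose, and section 8.7.2 treats myelosuppression as expected, so some contextual reading of 8.7 is needed. The general escalation rule itself carries no such qualifier. The version 3 sentence is therefore not used here as support for either side.

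Both replies show ambiguity; neither removes it.

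It is also fair that 8.7.3 is permissive and stepwise, with re-exposure at 200 before 220. Labs are drawn twice weekly for at least one week at any escalation (Appendix IV), and the day 1 and day 15 sampling is repeated (section 8.13). Section 8.6 gives a reason to push the dose: average troughs of 444 nM against a 680 nM target at 100 mg TID. These points stand. They slow, monitor or motivate the climb, but none sets a ceiling below 220.

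**Conclusion.** The wording of 8.7.3 permits a patient with grade 3–4 non-hematologic toxicity at 200 mg/m²/day (other than nausea, vomiting or diarrhea) to reach 220, 10% above the toxic dose, while 8.7 reserves 220 for patients without such toxicity. It is a gap in the wording that should be closed, and its practical reach is small.

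Three stronger readings are tempting and are not supported:

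- **A flat contradiction.** A reader might infer that the protocol intends this climb. The return-to-prior-level reading is open, so the text is ambiguous about intent.
- **An early risk.** A reader might take day 57 as the usual earliest time. It needs day 1 toxicity and no hold. About day 85 or later is the figure if next-cycle grading applies, and by then section 7.2 leaves very few candidates.
- **A rate.** A reader might divide the two transaminitis cases by the 16 patients in section 8.6 (2/16 = 12.5%) and apply it to the 14 planned. The two cases are described for this trial's dose, whereas the 16 come from two studies. Both cases took two CYP3A4 inhibitors, on flat dosing, and tolerated 80 mg TID. The ratio also counts reductions, not patients reaching 220. The documents give no rate at 200 mg/m²/day and none for the later conditions.

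The conclusion rests on reading the 8.7 condition without a current-dose qualifier. The timing takes 1 month as 28 days.

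**What to change.** Add to section 8.7.3:

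*After a reduction for grade 3 or 4 non-hematologic toxicity (other than nausea, vomiting or diarrhea), re-escalation will not exceed the lower of the dose level at which the toxicity occurred and 200 mg/m²/day; 220 mg/m²/day is available only to patients who meet the 8.7 escalation condition.*

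Repeat this beside the 220 row of the Appendix XV dosing sheet, since that is what the site works from. The clause still allows return to 200 after toxicity at 200. If the sponsor does mean 8.7.3 to override 8.7, it should say so and give the reason.

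The cost is one clause and one note, with no added visits, tests or patients. A very few patients without clinical benefit lose discretionary access to 220, including return to 220 after grade 3–4 toxicity at that level.

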8.7.4 Cycle Delays

A cycle of therapy may be delayed for a maximum of 28 days to allow recovery from toxicities. If drug has been held for total duration of 56 days or more, patient will be discontinued from study.

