6.2 Exclusion Criteria

- Absence of FLT3 activating mutation
- <5% blasts in blood or marrow at screening
- Concurrent chemotherapy, systemic immunosuppressants, or targeted anti-cancer agents, other than hydroxyurea
- Patient with concurrent severe and/or uncontrolled medical conditions that in the opinion of the investigator may impair the participation in the study or the evaluation of safety and/or efficacy
- HIV infection or active hepatitis B manifested as hepatitis B surface antigen (hepBs Atg) positivity or hepatitis C manifested as hepatitis C antibody positive.
- For post HSCT, subjects within 29 days of an allogeneic transplant, and/or are on an unstable dose of
 immunosuppressive drugs for management or prophylaxis of GVHD or have escalated therapy for GVHD
 within 14 days of starting study drug, and/or have >/=Grade 2 persistent non hematological toxicity related to
 the transplant or did not receive crenolanib prior to HSCT
- Evidence of lack of engraftment if post allogeneic transplant

- Unable to swallow pills
- Major surgical procedures within 14 days of Cycle 1 Day 1 administration of crenolanib.
- Unwillingness or inability to comply with protocol

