7.1 Summary of Treatment

The study will enroll AML patients with FLT3 D835 and/or other FLT3 activating mutations. Patients in relapse will be treated with crenolanib at 200mg/m²/day divided as three times a day (preferably every eight hours) continuously until they fulfill one of the criteria for study discontinuation (see Section 6.3) or proceed to allogeneic stem cell transplant.

Patients currently enrolled at 100mg TID (protocol v3.0) can be switched to the dosing based on BSA, see table 8.4, as per investigators discretion. If patients enrolled under v3.0 are continued on their current dose without BSA based dosing, continue study procedures from the current time point as outlined under Study Schedule (Appendix IV) of this version of the protocol (v4.0)

After allogeneic HSCT, patients who received crenolanib prior to transplant may resume crenolanib as maintenance on study post-transplant, if in remission at the same dose which was tolerated at the time of study drug hold prior to HSCT.

Patients who did not receive crenolanib preHSCT will not be able to receive crenolanib as maintenance therapy under this protocol.

Patients receiving less than 28 days of study dug as induction therapy will be replaced for efficacy evaluation. All patients will be assessed for toxicity

Study drug will be stopped if patients demonstrate evidence of relapsed disease as determined by the investigator.

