Counting Cycle Days: If drug is held or a dose is missed, the missed/held dose should not be made up. Dosing will resume with the next scheduled dose. The patient should enter in the diary the doses as missed. If drug is held or missed for a day or more, the cycle should continue as if uninterrupted. Counting days of a cycle should be ongoing without disruption. The start of cycle 1 is denoted by the ingestion of study drug. The scheduled procedures/visits should comply with the study calendar regardless of amount of study drug administered in a 28 day cycle.

Continuation of crenolanib after allogeneic transplantation as maintenance therapy:

Crenolanib will be held during the transplant period by stopping drug 72 hours prior to start of conditioning and resuming no sooner than 30 days post stem cell infusion.

For patients in CR/CRi after allogeneic transplant, crenolanib may be resumed at the same dose of crenolanib tolerated as induction when crenolanib was held. Patients will complete a daily diary to record the date, time and amount (number of tablets) of crenolanib taken and if it was taken either with or without food (Appendix III). Tablets should be swallowed whole and not be crushed or dissolved/

Patients may receive multiple cycles of treatment as described in Section 8.7.5. Follow up of patients on post-transplant crenolanib is outlined in section 8.2

The investigator or his/her designee is responsible for explaining the correct use of the investigational agent(s) to the patient/site personnel, verifying that instructions are followed properly, maintaining accurate records of study drug dispensing and collection, and returning all unused medication to AROG or its designee at the end of the study. Study medication that has been dispensed but remains unused at the end of the cycle is recorded by the site personnel and either safely discarded, if opened, or returned, if unopened.

Patients will be instructed to contact the investigator as soon as possible if they have a complaint or problem with the study drug so that the situation can be handled. If a patient vomits after drug ingestion, no additional tablets should be taken on that day. Missed doses will not be made up, and leftover drug should be returned to the study site upon patient follow up

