First dose reduction (-1)	180 mg/m ² /day
Second dose reduction (-2)	160 mg/m ² /day

For patients receiving maintenance crenolanib after allogeneic transplant: Start of maintenance crenolanib therapy is intended at the earliest time no sooner than 30 days but no longer than 90 days after allogeneic HSCT. Prerequisites for start of maintenance are a stable dose of immunosuppressive drugs for management or prophylaxis of GVHD or no escalation of therapy for GVHD within 14 days of starting study drug and/or have no more than Grade 2 persistent non hematological toxicity related to the transplant. Patients must have received crenolanib prior to HSCT to continue on to maintenance.

Maintenance therapy will start at the last dose tolerated during reinduction therapy. For example, if the patient was taking 180mg/m2/day prior to proceeding with HSCT, maintenance therapy will resume at 180mg/m2/day.

Dose reductions for non-hematologic toxicities except nausea, vomiting or diarrhea due to crenolanib will be done according to the schema in Table 8.5. For dose level reductions please refer to Table 8.6, and appendix XV. Dose reductions below 140 mg/m2/day are not planned and crenolanib will be stopped.

Table 8.5. Based on NCI CTCAE v4.03, Crenolanib Dose Reduction for Non-Hematologic Toxicities Post Allogeneic Transplant except Nausea, Vomiting, or Diarrhea related to study drug. Use toxicity grade at time of start of next planned cycle. Reassessment may be

performed weekly to determine when to restart drug or dose modify. A 28-day deferment window is allowed to assess toxicities.

Toxicity (NCI Criteria)	Dose modification for patients taking crenolanib post allogeneic transplant
Grade 1 or 2	No dose modification
Clinically significant or persistent grade 2 despite optimal therapy	Hold drug until toxicity resolves to baseline or grade 1 or less. Restart drug at same dose level (Table 8.6).
Grade 3 or 4	Hold drug until toxicity resolves to baseline or grade 1 or less. Restart drug at next lower dose level (Table 8.6).

Table 8.6. Dose adjustments of Crenolanib Post Allogeneic Transplant Maintenance therapy will start at the last dose level tolerated during reinduction therapy and dose adjustments made from that dose.

Current crenolanib dose:	Change crenolanib dose to:
100 mg PO TID*	80 mg PO TID
220 mg/m2/day	200 mg/m2/day
200 mg/m2/day	180 mg/m2/day
180 mg/m2/day	160 mg/m2/day
160 mg/m2/day	140 mg/m2/day

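### The post-transplant rules conflict on persistent Grade 2 toxicity and, read literally, on the 56-day hold limit, and no relapse assessment is scheduled off drug after the 30-day visit.

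*Combined protocol and SAP*

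**What the plan says.** **Toxicity limit for starting maintenance.** Section 8.7.1 lists as a prerequisite that patients "have no more than Grade 2 persistent non hematological toxicity related to the transplant". The exclusion in 6.2 written for post-HSCT subjects removes those who "have >/=Grade 2 persistent non hematological toxicity" from the transplant. Section 6.1 requires recovery from non-hematological toxicity of prior therapy, HSCT included, to Grade 1 or less.

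**Hold limit.** Section 8.7.4 (Cycle Delays) has two sentences. The first is "A cycle of therapy may be delayed for a maximum of 28 days to allow recovery from toxicities". The second is "If drug has been held for total duration of 56 days or more, patient will be discontinued from study", with no reason for the hold and no exception.

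**Transplant pause.** Three sections call it a hold. Section 7.1 has patients resume "at the same dose which was tolerated at the time of study drug hold prior to HSCT". Section 8.3 says "Crenolanib will be held during the transplant period by stopping drug 72 hours prior to start of conditioning", and 8.7 says "Crenolanib will be held starting 72 hours prior to start of planned conditioning for HSCT". Sections 8.3 and 8.7 require at least 30 days off drug after infusion. Section 8.7.1 sets the window: "Start of maintenance crenolanib therapy is intended at the earliest time no sooner than 30 days but no longer than 90 days" after HSCT.

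**Follow-up off drug.** Section 6.3.1 stops the study schedule at allogeneic HSCT and asks for survival data where possible. Section 8.12 applies the schedule to patients receiving drug, restarts the calendar at cycle 1 when drug is resumed after transplant, and asks for survival follow-up of everyone who stops drug for any reason. The Synopsis and 11.1.7 provide one 30-day follow-up. Duration of response (DoR) and PFS are listed primary objectives (1.1) and are to be listed and summarized by Kaplan-Meier (10.3, 10.3.7).

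**The concern.** Maintaining remission after transplant is one of the purposes stated in the Synopsis, so the rules for pausing and restarting drug should give a site one answer.

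- The toxicity prerequisite is a safety threshold, and two parts of the protocol put it one grade apart for the same decision.
- A discontinuation rule that counts every hold would, on its face, remove patients whom the restart window is meant to keep.
- DoR and PFS both need a relapse or progression date, or a last date known free of it. Once a patient is off drug, survival is the only outcome the plan asks for after the 30-day visit, and no section says how these endpoints are censored. DoR is further confined to the responders among 14 evaluable patients, so a few unknown relapse dates could move its Kaplan-Meier curve.

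**Working it through.** **1. Toxicity limit, side by side**

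| Persistent non-hematological transplant toxicity | 8.7.1 | 6.2 | 6.1 |
|---|---|---|---|
| Grade 1 or less | admits | admits | admits |
| Grade 2 | admits | excludes | excludes |
| Grade 3 or more | excludes | excludes | excludes |

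The conflict is confined to persistent Grade 2. Inclusion item 7 of Appendix I also sets Grade 1 as the limit, but omits the non-hematological qualifier.

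**2. The 56-day limit against the restart window**

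Inputs: the hold starts 72 hours (3 days) before conditioning (8.3, 8.7); restart is permitted from day 30 to day 90 (6.1, 8.7.1), which is 90 − 30 + 1 = 61 calendar days; the limit is 56 days or more (8.7.4). The length of conditioning, c, is not given. I show c = 0 as the most lenient case, and 4 and 8 days as assumptions.

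Hold at restart day R = 3 + c + R. The limit is reached at R = 53 − c. Barred days = 90 − (53 − c) + 1 = 38 + c.

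| c (days) | Hold at day-30 restart | Hold at day-90 restart | First barred day | Barred days of 61 |
|---|---|---|---|---|
| 0 | 33 | 93 | 53 | 38 |
| 4 (assumed) | 37 | 97 | 49 | 42 |
| 8 (assumed) | 41 | 101 | 45 | 46 |

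If the total is cumulative over the study, one 28-day delay allowed by 8.7.4 plus a day-30 restart gives 28 + 33 = 61 days at c = 0 (65 at c = 4, 69 at c = 8), so even the earliest restart is barred. The earlier hold that is just enough to bar a day-30 restart is 56 − 33 = 23 days at c = 0.

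**3. Who has a scheduled relapse assessment**

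- *Patients who restart:* covered. Sections 7.1 and 8.3 require remission at restart, and 8.12 restarts the calendar, including marrows.
- *Patients in the transplant gap:* 6.3.1 stops the schedule; survival only.
- *Patients who never restart, or who stop drug for another reason:* the 30-day visit, which includes physical examination and hematology (Appendix IV), then survival contacts with no stated interval. Section 11.1.7 adds 30-day checks only while drug-related toxicity persists.

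The timing of the 30-day visit depends on its starting point. Counted from the last dose before transplant (Synopsis), it falls 30 − 3 − c days after infusion: day 27 at c = 0 (22–32 with the ± 5 days in 11.1.7), day 23 at c = 4 (18–28), day 19 at c = 8 (14–24). That is around or before the first permitted restart. Section 11.1.7 counts from discontinuation of treatment instead. If that is declared only when restart is abandoned, the visit falls later, on a date the documents do not fix.

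**The case against.** *On the hold limit.* The heading and first sentence of 8.7.4 concern toxicity delays, other sections specifically authorize the transplant pause, and hold length is not among the discontinuation reasons in 6.3.1. Reading every line literally would also let the 6.2 exclusion of patients with under 5% blasts bar everyone in remission from restarting, which cannot be intended. This largely stands as to intent. It does not make the text clear: 8.9 qualifies a hold by its reason when that matters, and the 56-day sentence does not.

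*On Grade 2.* One could say that 6.1 and 6.2 govern first entry and 8.7.1 governs restart. But the 6.2 bullet is written for post-HSCT subjects and also excludes those without crenolanib before transplant, so it addresses the same restart decision. Section 6.3.1 requires the enrollment criteria to be followed explicitly, which favours the stricter limit in practice but leaves 8.7.1 contradicting it.

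*On relapse.* Remission is checked before restart, so a relapse in the gap would normally surface when restart is considered. The 30-day visit could reveal an early relapse, and deaths come in through survival follow-up. All of this stands. Survival-only follow-up and the missing censoring rule apply to every patient off drug, so the gap is a general one and partly a matter of missing detail.

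*On weight.* Section 10.3 names response rate alone as the primary end-point, and DoR and PFS are descriptive. That is correct and limits the consequence.

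**Conclusion.** The point holds in three parts of unequal strength.

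- The Grade 2 conflict is direct, concerns a safety threshold, and needs no assumption.
- The 56-day conflict holds on the literal text: at least 38 of 61 permitted restart days, rising with the length of conditioning. Toxicity holds were probably meant.
- No relapse assessment is scheduled off drug beyond the 30-day visit, and no censoring rule covers the resulting unknown status.

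A reader might infer more than the documents support:

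- *That maintenance after transplant is unworkable, or that about 62% of patients (38/61) would be lost.* A day-30 restart with no long earlier hold totals 33 to 41 days for c of 0 to 8 and complies. The fraction counts calendar days, and 8.7.1 intends restart at the earliest time. The share of patients affected is unknown.
- *That relapse goes uncaptured after transplant.* Patients who restart return to the full calendar. For the others the defect is the lack of a scheduled assessment, and relapse may still be found clinically.
- *That the GVHD wording in Appendix I is a further eligibility conflict.* Exclusion item 7 there is stricter than 6.2, but the checklist is labelled as taken from the approved protocol and its last inclusion item carries the 14-day wording of 6.1. It is a clerical slip.

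None of these points affects the response-rate decision rule.

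**What to change.** 1. In 8.7.1, change the prerequisite to no more than Grade 1 persistent non-hematological transplant toxicity, to match 6.1 and 6.2.
2. In 8.7.4, state that the 56-day limit applies to holds for toxicity and excludes the planned HSCT hold. All 61 permitted restart days then become usable.
3. In 6.3.1 and 8.12, at the survival contacts already required for all patients off drug, also record from routine clinical records the date of relapse or progression, or the date last known in remission (for PFS in a patient never in remission, last known progression-free). In 10.3.7, censor DoR and PFS at that last date when status is unknown.
4. Clerical: align exclusion item 7 of Appendix I on GVHD with 6.2.

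Items 1, 2 and 4 are wording only. Item 3 adds a small records burden. The plan gives no contact interval; if contacts were every 12 weeks (my assumption, equal to the three-cycle marrow interval in 8.2), the upper bound is 3 × 365 / 84 ≈ 13 checks per patient over the 3-year study. No visits, marrows or patients are added. The drawback is that relapse dates from routine records are less exact than dates from scheduled marrows.
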